The AMG 596 start dose based on preclinical evaluations for the estimation of the MABEL is [REDACTED] µg/day. Further pre-specified nominal AMG 596 doses for potential use in any dose escalation Arm are [REDACTED] µg/day. The dose level review team (DLRT) may consider treating at intermediate doses if required. If the MTD or a biological active dose considered the RP2D is not reached within the pre-planned nominal dose range, the DLRT may decide to expand the nominal dose range to dose levels [REDACTED] µg/day after careful consideration of all available safety, laboratory, and PK information. The preliminary estimate of the RP2D/MTD of AMG 596 will be done initially in subjects with recurrent disease (Group 1) and separately in subjects with maintenance treatment after SoC in newly diagnosed disease (Group 2) and separately for AMG 596 monotherapy and in combination with AMG 404. If the same AMG 596 doses are to be explored in monotherapy and in combination, the monotherapy cohort must be completed before enrollment in the combination cohort. In the multiple subject cohorts, a safety observation window of at least 72 hours must apply between start of subjects 1, 2 and 3 of each dose escalation cohort. Intra-subject dose escalation will be allowed to higher AMG 596 dose levels in subsequent treatment cycles

Approved

once a higher dose has been deemed safe by the DLRT. Subjects who do not proceed to a higher dose may continue at the original dose.

Group 1, Recurrent Disease

- *Dose Escalation in single subject cohorts*
 - AMG 596 monotherapy: In first cohorts AMG 596 will be administered as a cIV infusion for [REDACTED] at escalating doses with N=1 per cohort. In the single subject cohorts, only a limited number of subjects will be enrolled at dose levels anticipated to be lower than those at which visible pharmacodynamics activity including adverse events related to AMG 596 therapy will be expected. In addition, the investigator together with the subject will decide on subsequent treatment duration carefully. Subjects are allowed to stay on study in [REDACTED] cycles until discontinuation criteria apply.
 - Combination of AMG 596 with AMG 404: The starting dose of AMG 596 is [REDACTED] µg/day administered in [REDACTED] cycles and the defined AMG 404 dose is [REDACTED] mg every 4 weeks.
 - The cohort size will be increased to N=2-4 subjects (= Start of multiple subject cohorts) after observation of

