 - Treatment-related adverse events of common terminology criteria for adverse events (CTCAE 4.0) grade 2 or higher and/or
 - Quantifiable cytokine levels in blood or CSF above baseline
- *Dose Escalation in multiple subject cohorts:*
 - Subjects in the first multiple subject cohort receive the same dose as the last single subject cohort.
 - All subjects receive AMG 596 in [REDACTED] infusion cycles until treatment discontinuation criteria apply.

It is anticipated that dose-escalation will proceed according to the pre-planned nominal doses though intermediate dose levels may be used if required after reviewing all available safety data. When a first DLT is observed, the Bayesian logistic regression model (BLRM) will be used to guide dose level selection (Neuenschwander, Branson, & Gsponer, 2008). The cohort size will be N=2-4 subjects. On a limited basis, after agreement between the investigator and medical monitor, one additional subject may be allowed to be enrolled if the subject has been determined to be eligible and the cohort has been filled. In this case, all five subjects will be reviewed and assessed in the Dose Level Review Meeting (DLRM). After each cohort, the model's recommended MTD dose level for evaluation is the dose level with the highest probability of the target toxicity probability interval (TPI), but with a less than 0.25 probability of an excessive or unacceptable TPI. The target TPI is (0.20,

0.33], and TPIs of (0.33, 0.60] and (0.60, 1.00] are defined as excessive and unacceptable, respectively. The actual dose selected at each dose decision may be at or below the model's recommended dose as determined by the DLRT after considering all information. Dose escalation will be completed when any of the following occurs:

- The maximum total sample size of N=45 DLT evaluable subjects (including single subject cohorts) is reached for AMG 596 monotherapy or N=30 DLT evaluable subjects for AMG 596 in combination with AMG 404.
- The BLRM model recommends the same dose level at least 2 times and that at least 6 subjects have been treated at the recommended RP2D/MTD dose level. If step-dosing required, this stopping criterion applies separately to each period.
- The highest planned dose level is reached without any DLTs being observed

Group 2, Maintenance Treatment after SoC in Newly Diagnosed Disease

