- A first cohort will start after observation of a first objective antitumor response in Group 1 subjects with recurrent EGFRvIII-positive glioblastomas or malignant glioma. The starting dose of AMG 596 monotherapy in Group 2 will be decided by DLRT and will be the current highest dose deemed safe of Group 1. Treatment may consist either of [REDACTED] dose AMG 596 cIV [REDACTED] or step-dosing as established for recurrent disease. Further treatment cycles with [REDACTED] between cIV infusions will be provided until any of the treatment discontinuation criteria apply.
- The starting dose of AMG 596 in combination with AMG 404 for Group 2 will be one dose level below the selected start dose for AMG 596 monotherapy and an AMG 404 dose of [REDACTED] mg.
- The BLRM will be used to guide dose level selection. The cohort size will be N=2-4 subjects. The actual dose selected at each dose decision may be at or below the model's recommended dose as determined by the DLRT after considering all information.
- Dose escalation in Group 2 will be completed when any of the following occurs:
 - The maximum sample size of N=15 DLT evaluable subjects is reached for AMG 596 monotherapy or N=20 DLT evaluable subjects for the AMG 596 in combination with AMG 404.
 - At least 6 subjects have been treated at the recommended RP2D/MTD dose level
 - The highest pre-specified nominal dose level is reached without any DLTs being observed

Part 2: Dose Expansion

The purpose of dose expansion will be to further explore safety and to evaluate preliminary antitumor-activity in subjects with recurrent disease (Group 1) and in

subjects with maintenance setting (Group 2). It is anticipated that 15 subjects will be enrolled to Group 1 in Arm 1 and Arm 2, respectively. Up to 25 subjects will be enrolled to Group 2 in Arm 1 and Arm 2, respectively.

In Group 2 both for Arm 1 and Arm 2, the objective response rate (ORR) of interest is 20% or higher while an ORR of 5% or less is considered insufficient antitumor-activity. For each arm, the ORR in Group 2 will be initially evaluated after 10 subjects are treated and have been evaluated at the first imaging scan or have dropped out before that. If ORR is lower than 5%, enrollment may be terminated due to futility. Otherwise, the ORR will be evaluated for additional new subjects and the futility stopping rules are calculated using a Bayesian predictive probability design (see [Section 10.2](#) for details).

[figure not shown]

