10.2 Sample Size Considerations

It is anticipated that up to 190 subjects will be enrolled in the study. It is anticipated that up to 100 subjects will be enrolled to Arm 1 in this study and up to 90 subjects will be enrolled to Arm 2 in this study.

For Group 1 (recurrent disease), the following are the planned sample sizes.

- In dose escalation, up to 45 DLT-evaluable subjects will be enrolled to monotherapy Arm 1 and up to 30 DLT-evaluable subjects to combination Arm 2
- In dose expansion, up to 15 subjects will be enrolled to monotherapy Arm 1 and up to 15 subjects to combination Arm 2.

For Group 2 (maintenance setting), the following are the planned sample sizes.

- In dose escalation, up to 15 DLT-evaluable subjects will be enrolled to monotherapy Arm 1 and up to 20 DLT-evaluable subjects to combination Arm 2
- In dose expansion, up to 25 subjects will be enrolled to monotherapy Arm 1 and up to 25 subjects to combination Arm 2

The sample sizes in dose escalation are based on practical considerations and it is consistent with conventional oncology studies with the objective to identify the RP2D/MTD. With 2 subjects per cohort, there is a 19-56% probability of observing at least one DLT for a cohort if the true DLT rate is 10-33% and with 6 subjects per cohort, the probability is 47-91%.

For Group 1 (recurrent disease) in each respective arm (monotherapy and combination), the respective sample sizes of the dose expansion cohorts are based on practical considerations. With 21 subjects treated at the RP2D/MTD (6 from dose escalation and 15 from dose expansion) in an arm, there is a 66% probability of observing an adverse event with 5% incidence rate. For an ORR of 20%, the probability of observing the OR in at least 4 subjects would be 63%. The estimated ORR and exact 80% CI for 4 responses is 19% and 9%-35% respectively.

For Group 2 (maintenance setting) in each respective arm (monotherapy and combination), the sample sizes in the respective dose expansion arm are based on a Bayesian predictive probability design (Lee, 2008). For both arms, the ORR of interest is 20% or higher while an ORR of 5% or less is considered insufficient antitumor-activity. The maximum sample size per arm is 31 subjects (6 from dose escalation and 25 from dose expansion). Futility will be assessed initially after treating 10 subjects for at least 6 months and continuously for each additional subject afterwards. If ORR is lower than

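### Escalation can close at the top dose after one cohort of 2–4 subjects, but the 21- and 31-subject designs count 6 escalation subjects at that dose

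*Protocol*

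**What the plan says.** **Completion of escalation (Protocol 3.1, repeated in the synopsis).** For Group 2, "Dose escalation in Group 2 will be completed when any of the following occurs", and three alternatives follow: the cap on DLT-evaluable subjects, "At least 6 subjects have been treated at the recommended RP2D/MTD dose level", and "The highest pre-specified nominal dose level is reached without any DLTs being observed". Group 1 has the same structure. There the 6-subject minimum belongs to the criterion on repeated model recommendations, and a separate criterion is "The highest planned dose level is reached without any DLTs being observed". In neither group does the highest-dose criterion carry a number of subjects.

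**Cohort size (Protocol 3.1).** "The cohort size will be N=2-4 subjects" applies in Group 2 and to the multiple-subject cohorts of Group 1. A fifth subject is possible in Group 1 on a limited basis.

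**Sample size (Protocol 10.2).** Group 1: "With 21 subjects treated at the RP2D/MTD (6 from dose escalation and 15 from dose expansion) in an arm". Group 2: "The maximum sample size per arm is 31 subjects (6 from dose escalation and 25 from dose expansion"). Expansion is up to 15 and up to 25 per arm.

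**Futility table (Protocol 10.2).** The rows are 10 subjects (0 responders), 19 (1 or fewer), 26 (2 or fewer) and 31 (3 or fewer). The stated type I error is 0.05 at an ORR of 5%, and the stated power is 0.8 at 20%.

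SAP sections 3.1 and 3.2 carry the same any-of rule, the same highest-dose criterion and the same totals of 21 and 31. The SAP still has Group 2 cohorts of 4–6, so a single cohort could have supplied the 6. Under the protocol's current 2–4 it cannot.

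**The concern.** The sample-size section treats as given something that the completion rule does not secure. The 6-subject minimum is one of several alternative triggers, so meeting the highest-dose criterion makes it irrelevant. The missing subjects cannot be recovered later, because expansion has its own ceiling.

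The route is realistic. Section 2.5.3.1 expects systemic toxicity from the drug's mechanism to be limited. Section 3.1 provides for the MTD not being reached in the nominal range. Group 2 monotherapy starts at the highest dose then deemed safe in Group 1; if that is already the top nominal dose, one cohort without a DLT closes Group 2 escalation. In Group 1 the dose-toxicity model is brought in only after a first DLT, so on this route it does not require more subjects either.

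Two things are at stake. The operating characteristics in section 10.2 would describe a larger study than the one run. A Group 2 arm would also finish at a size for which no final threshold is written, leaving the choice open until the responses are known.

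**Working it through.** **1. Reproduce the stated Group 2 figures at N = 31.** Inputs: the four table rows, ORR 5% and 20%, and acceptance at 4 or more of 31 (the complement of the last row). The number of responders is carried forward by binomial increments, and paths at or below the boundary are removed at each row.

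| ORR | Stop at 10 | Stop at 19 | Stop at 26 | Fail at 31 | Accept |
|---|---|---|---|---|---|
| 5% | 0.5987 | 0.1986 | 0.0985 | 0.0544 | 0.0497 |
| 20% | 0.1074 | 0.0360 | 0.0255 | 0.0283 | 0.803 |

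These match the stated 0.05, 0.8 and 60% stop at 10. At an ORR of 5%, expected N = 10×0.5987 + 19×0.1986 + 26×0.0985 + 31×(0.0544 + 0.0497) ≈ 15.55. Subtracting 6 gives 9.55, which is the stated 9.6. That figure, too, needs the 6 escalation subjects.

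**2. Group 2 with one top-dose cohort.** Maximum N = cohort + 25, so 2, 3 or 4 gives 27, 28 or 29. The table rows up to 26 are unchanged and 4 or more responders is kept at the final N.

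| Final N | Type I error (ORR 5%) | Power (ORR 20%) |
|---|---|---|
| 27 | 0.037 | 0.762 |
| 28 | 0.041 | 0.776 |
| 29 | 0.044 | 0.787 |
| 30 | 0.047 | 0.796 |
| 31 (plan) | 0.050 | 0.803 |

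**3. Group 1.** Chance of seeing at least one adverse event of 5% incidence = 1 − 0.95^n. Chance of at least 4 responses at ORR 20% = P(X ≥ 4) for X ~ Binomial(n, 0.2). One cohort of 2–4 plus 15 gives n = 17–19; an exceptional fifth subject gives 20.

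| n | 5% AE seen | At least 4 responses |
|---|---|---|
| 17 | 58% | 45% |
| 18 | 60% | 50% |
| 19 | 62% | 54% |
| 20 | 64% | 59% |
| 21 (plan) | 66% | 63% |

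The n = 21 row reproduces the plan. Every stated figure checked is arithmetically right, given the 6 subjects.

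**The case against.** Several points on the other side have force.

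- **Discretion exists.** Section 10.4.2 lets the dose level review team repeat or expand a cohort, so a shortfall is possible, not certain. Nothing requires the team to do so.
- **The ORR decision is not the primary purpose.** ORR is a secondary endpoint, the table is a futility guideline, termination is optional, and the reported 80% exact interval works at any N. The totals are described as maxima, and Group 1's size as resting on practical considerations. This limits the severity. But section 10.2 does claim a type I error and a power, and they should hold on the routes the protocol allows.
- **Intra-subject escalation.** Subjects moved up to the RP2D/MTD might count towards the 6. The documents do not say.

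Four stronger readings might be inferred, and none is supported.

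- *Escalation could close on a single subject.* Cohorts "at escalating doses with N=1 per cohort" exist only in Group 1, at doses expected to lie below visible pharmacodynamic activity. They end at the first related grade 2 event or quantifiable cytokine rise, and section 2.5.3.2 already reports pharmacodynamic effects. The case is remote.
- *Type I error doubles to about 0.10.* This needs survival of the n = 26 row (3 or more responders) to count as acceptance, which gives 0.104 and 0.831. The plan never says so.
- *All of section 10.2 fails.* The DLT-detection probabilities and Tables 19 and 20 do not use the 6 subjects.
- *A poorly characterised dose goes unchecked into expansion.* Lower cohorts precede the top dose, expansion has interim safety reviews after 5 recurrent and 10 maintenance subjects with possible dose revision, and there is an enrollment hold for related grade 4 or higher events.

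**Conclusion.** The point holds as a mismatch between the completion rule and the sample-size basis. It is not an arithmetic error. On a route that section 3.1 permits, Group 2 ends 2–4 subjects short of 31 and Group 1 ends 2–4 short of 21.

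In Group 2 the loss is modest if the threshold of 4 is kept: power falls by 1.6 to 4.1 percentage points and type I error stays below 0.05. The weaker spot is that no final threshold is written for N between 27 and 30. In Group 1 the response figure drops more, by 8 to 18 percentage points.

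This assumes that one cohort of 2–4 closes escalation, that it is neither repeated nor expanded, that expansion fills to its cap, and that subjects escalated within the study are not counted. Treating 4 or more of 31 as the acceptance rule is an inference from the table, but it is the reading that reproduces 0.05 and 0.80. The item is a moderate reconciliation.

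**What to change.** Reconcile the highest-dose completion criterion (Protocol 3.1 and synopsis, both groups; SAP 3.1) with the 6 subjects that section 10.2 relies on. Either the 6 are secured within the existing escalation caps, or section 10.2 and SAP 3.2 stop assuming them. Which of these suits the escalation is for the sponsor to decide.

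In either case, add to section 10.2:

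- that the Group 2 final threshold is 4 or more responders at the N actually reached, with type I error and power for N = 27–31;
- the two Group 1 probabilities for n = 17–21;
- whether subjects who reach the RP2D/MTD by intra-subject escalation count towards the 6.

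Cost: wording and two short tables. If the 6 are secured, 2–4 more subjects (6 minus a cohort of 4 or 2) per affected arm and group, so at most 4 × 4 = 16 if all four arm-by-group combinations took this route with cohorts of 2. If they are not secured, the only cost is slightly less favourable stated figures.

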3.2 Number of Sites

This study will be conducted at approximately 12 or more sites in the United States, Australia and Europe. Additional countries or sites may be added if deemed necessary. Sites that do not enroll subjects into an open cohort within 6 months of site initiation may be closed or replaced.

3.3 Number of Subjects

Participants in this clinical investigation shall be referred to as “subjects”.

It is anticipated that around 190 subjects will be enrolled in the study.

It is anticipated that up to 100 subjects will be enrolled to Arm 1 in this study and up to 90 subjects will be enrolled to Arm 2 in this study.

For Group 1 (recurrent disease), the following are the planned sample sizes.

- In dose escalation, up to 45 DLT-evaluable subjects will be enrolled to monotherapy Arm 1 and up to 30 DLT-evaluable subjects to combination Arm 2
- In dose expansion, up to 15 subjects will be enrolled to monotherapy Arm 1 and up to 15 subjects to combination Arm 2.

For Group 2 (maintenance setting), the following are the planned sample sizes.

- In dose escalation, up to 15 DLT-evaluable subjects will be enrolled to monotherapy Arm 1 and up to 20 DLT-evaluable subjects to combination Arm 2
- In dose expansion, up to 25 subjects will be enrolled to monotherapy Arm 1 and up to 25 subjects to combination Arm 2.

The rationale for the number of subjects is provided in [Section 10.2](#).

Replacement of Subjects

Ineligible subjects (ie, subjects who were exposed to investigational product (IP) but after starting AMG 596 treatment were found to be ineligible) may be replaced. During dose escalation, a subject that is not DLT-evaluable will be replaced with another subject to the same dose level. A DLT-evaluable subject is defined as:

- Subject in the [REDACTED] cycle receiving a complete first cycle with 100% of the planned doses of investigational product, or
- Subject in the [REDACTED] cycle receiving at least 90% of the planned doses of investigational products, or
- Subject that has experienced a DLT.

Subjects will not be replaced after end of the DLT period.

Approved

3.4 Estimated Study Duration

The duration of this study will be approximately 4.5 years, with about 42 months for enrollment (a maximum of 30 months for the dose escalation cohorts, and 12 months for the dose expansion cohort) and 12 months protocol treatment period.

3.4.1 Study Duration for Subjects

It is anticipated that an individual subject will participate in the study for approximately 8 months including an effective screening period lasting 14 days, a treatment period lasting approximately 4 to 6 months, and a safety follow up period lasting 30 days (+/- 7 days). Additionally, there is a long term follow up for up to 12 months from treatment initiation. The actual duration for individual subjects will vary depending upon tolerability of AMG 596, evidence of clinical progression, and willingness to participate in the study.

In the event that a subject demonstrates clinical benefit from therapy, he or she may continue treatment with AMG 596 until he or she experiences an unacceptable adverse event, clinically significant disease progression, or he or she wishes to withdraw consent.

The safety follow-up study visit (SFUP) should occur 30 days (+/- 7 days) after the last dose of AMG 596 or prior to the initiation of other therapy, whichever occurs first. End of study for an individual subject is defined as the date of the final long-term follow up study visit (LTFU) when assessments and procedures are performed.

3.4.2 End of Study

Primary Completion: the time when the last subject is assessed or receives an intervention for the purposes of final collection of data for the primary analysis; a primary analysis will be performed for each group separately when target enrollment in Part 1 and Part 2 is complete and each subject either completes 6 months on study or withdraws from the study.

End of Study: the time when the last subject is assessed or receives an intervention for evaluation in the study. The final analysis will occur at this time.

4. SUBJECT ELIGIBILITY

4.1 Inclusion Criteria

101. Subject has provided written informed consent prior to initiation of any study-specific activities/procedures
102. Male or female, of at least 18 years of age

103. Eastern Cooperative Oncology Group (ECOG, [Appendix F](#)) Performance Status of ≤ 1
104. Life expectancy of at least 3 months, in the opinion of the investigator.
105. Must have pathologically documented, and definitively diagnosed World Health Organization (WHO) grade 4, glioblastoma or lower grade malignant gliomas with EGFRvIII positive tumor
106. Must have recurrent disease confirmed by MRI (Group 1) or completed SoC therapy such as surgery with adjuvant radiochemotherapy with or without maintenance temozolomide according to local standards for newly diagnosed disease (Group 2)
107. Group 1 subjects must have ≥ 1 index lesion by modified RANO criteria ([Appendix D](#)), exemption: non-measurable disease is allowed for subjects with re-surgery (surgery for recurrent disease) before start of screening; Group 2 subjects must have radiographically measurable disease or non-measurable disease by modified RANO criteria or both at the time of enrollment are allowed:
 - Bidimensionally measurable, contrast-enhancing lesions with clearly defined margins by MRI with perpendicular diameters of at least 10 mm x 10 mm and noted in more than one imaging slice
 - Imaging must be performed within 14 days of enrollment. Subject can be on stable dose steroid medication (systemic corticosteroid doses of ≤ 2 mg of dexamethasone (or equivalent) per day after consultation with Sponsor) for at least 5 days immediately before and during imaging study
108. Confirmed EGFRvIII positivity from pre-screening or confirmation at time of study enrollment required if prior treatment included EGFRvIII – or amplified EGFR- targeted therapy (one test sufficient, please refer to [Section 7.2.1](#))
109. Archived tumor tissue from initial diagnosis or subsequent relapse for submission to central review
110. Hematological function as follows:
 - Absolute neutrophil count (ANC) $> 1500/\text{mm}^3$ ($1.5 \times 10^9/\text{L}$)
 - Platelet count $> 100,000/\text{mm}^3$ ($100 \times 10^9/\text{L}$)
 - White blood cell (WBC) count $> 3 \times 10^9/\text{L}$
 - Hemoglobin > 9.0 g/dL
111. Renal function as follows: serum creatinine < 2.0 mg/dL and estimated glomerular filtration rate ≥ 60 mL/min/1.73 m² by MDRD and urine protein quantitative value of < 30 mg/dL in urinalysis or $\leq 1+$ on dipstick

Approved

112. Hepatic function as follows:
- Aspartate aminotransferase (AST) and Alanine aminotransferase (ALT) ≤ 3.0 x upper limit of normal (ULN)
 - Bilirubin ≤ 1.5 x ULN (unless considered due to Gilbert's syndrome or hemolysis)

